ATR-101 250-mg and 500-mg tablets for oral administration, one tablet twice per day for the 250 mg and 500 mg BID doses, respectively; and two 500-mg tablets twice per day for the 1000 mg BID dose

Duration of Treatment:

8 weeks in the open-label dose-escalation period and up to 4 weeks in the double-blind randomized withdrawal period or the additional open-label period

Reference Therapy, Dosage and Mode of Administration:

Placebo matching tablets for the ATR-101 500-mg tablets during the double-blind randomized withdrawal period

Study Endpoints:

Primary Efficacy Endpoint:

- The proportion of subjects with either a normal 24-hr UFC or a reduction in 24-hr UFC of $\geq 50\%$ relative to their baseline value at the end of the double-blind randomized withdrawal period

Secondary Efficacy Endpoints: The secondary efficacy endpoints will include the following. Unless otherwise specified in the Statistical Analysis Plan, the endpoints will be evaluated for each post-baseline visit, at the end of the open-label dose-escalation period and at the end of the double-blind randomized withdrawal period, for the ITT population as a whole and for each baseline UFC stratum.

- The proportion of subjects with a normal 24-hr UFC at the end of the double-blind randomized withdrawal period
- The proportion of subjects with a reduction in 24-hr UFC of $\geq 50\%$ relative to their baseline value at the end of the double-blind randomized withdrawal period
- The proportion of subjects with a normal 24-hr UFC at the end of the open-label dose-escalation period and at the end of the additional open-label dosing period
- The proportion of subjects with a reduction in 24-hr UFC of $\geq 50\%$ relative to their baseline value at the end of the open-label dose-escalation period and at the end of the additional open-label dosing period
- The change and percentage change in the 24-hr UFC from randomization at the end of the double-blind randomized withdrawal period
- The change and percentage change in the 24-hr UFC from baseline at the end of the open-label dose-escalation period and at the end of the additional open-label dosing period
- The proportion of subjects with a normal late night salivary cortisol at the end of the double-blind randomized withdrawal period
- The proportion of subjects with a normal late night salivary cortisol at the end of the open-label dose-escalation period and at the end of the additional open-label dosing period

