4.2. Exclusion Criteria

Subjects who meet any of the following criteria will be excluded from participation in the study:

1. Pseudo-Cushing's syndrome, cyclic Cushing's syndrome or current iatrogenic Cushing's syndrome

2. Subjects who are considered candidates for surgical treatment of Cushing's syndrome, unless it is clearly documented that the subject has refused such surgery or that surgery cannot be scheduled for at least the anticipated duration of the study
3. Normal late night salivary cortisol value during screening unless the subject's history clearly demonstrates that he or she does not have pseudo-Cushing's or cyclic Cushing's. If the subject has a normal late night salivary cortisol, and the PI feels the subject does not have pseudo-Cushing's or cyclic Cushing's, the subject may be enrolled with approval of the medical monitor
4. Normal 24-hr UFC during screening (this would be suggestive of cyclic Cushing's)
5. Radiotherapy of the pituitary within 6 months prior to or during screening
6. For subjects with pituitary Cushing's syndrome, any compression of the optic chiasm or the presence of a tumor within 2 mm of the optic chiasm on the most recent pituitary MRI prior to or during screening
7. Use of or medical requirement for any of the following medications within the timeframes specified below prior to collection of the first 24-hr UFC during Screening and throughout study participation (see Section 5.11 for additional prohibited and restricted medications):
 - Inhibitors of steroidogenesis (ketoconazole, metyrapone): 1 week
 - Pituitary-directed agents: Dopamine agonists (bromocriptine, cabergoline) and PPAR γ agonists (rosiglitazone or pioglitazone): 4 weeks
 - Octreotide LAR, Lanreotide SR and Lanreotide autogel: 14 weeks
 - Octreotide (immediate release formulation): 1 week
 - Pasireotide: 4 weeks
 - Mitotane: 26 weeks
 - Mifepristone: 3 weeks
8. Uncontrolled diabetes mellitus, as evidenced by HbA1c > 9.0% at screening
9. Uncontrolled hypertension, defined as systolic blood pressure > 160 mmHg or diastolic blood pressure > 90 mmHg during screening. Note: if appropriate, subjects may have blood pressure medications adjusted and blood pressure reassessed at an unscheduled visit prior to Visit T1.
10. Any history of gastric or small intestinal surgery or any current disease that causes malabsorption. Note: irritable bowel syndrome is acceptable for inclusion

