9.6.1.2. Secondary Efficacy Endpoints

The secondary efficacy endpoints will include the following. If the data allow, unless otherwise specified in the Statistical Analysis Plan, the endpoints will be evaluated for each post-baseline

visit, at the end of the open-label dose-escalation period and at the end of the double-blind randomized withdrawal period, for the ITT population as a whole and for each baseline UFC stratum.

- The proportion of subjects with a normal 24-hr UFC at the end of the double-blind randomized withdrawal period
- The proportion of subjects with a reduction in 24-hr UFC of $\geq 50\%$ relative to their baseline value at the end of the double-blind randomized withdrawal period
- The proportion of subjects with a normal 24-hr UFC at the end of the open-label dose-escalation period and at the end of the additional open-label dosing period
- The proportion of subjects with a reduction in 24-hr UFC of $\geq 50\%$ relative to their baseline value at the end of the open-label dose-escalation period and at the end of the additional open-label dosing period
- The change and percentage change in the 24-hr UFC from randomization at the end of the double-blind randomized withdrawal period
- The change and percentage change in the 24-hr UFC from baseline at the end of the open-label dose-escalation period and at the end of the additional open-label dosing period
- The proportion of subjects with a normal late night salivary cortisol at the end of the double-blind randomized withdrawal period
- The proportion of subjects with a normal late night salivary cortisol at the end of the open-label dose-escalation period and at the end of the additional open-label dosing period
- The change and percentage change in the late night salivary cortisol from randomization at the end of the double-blind randomized withdrawal period
- The change and percentage change in the late night salivary cortisol from baseline at the end of the open-label dose-escalation period and at the end of the additional open-label dosing period
- The change and percentage change from baseline in blood hormone levels, including 11-DOC, 17-OHP, A, A4, ACTH, cortisol, DHEA, DHEAS, free T, P, renin, SHBG and total T
- The change from baseline in fasting glucose, insulin, lipid panel, systolic blood pressure, diastolic blood pressure and BMI

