9.6.2.2. Secondary Efficacy Endpoints

No further adjustments for multiple group comparisons, multiple additional endpoints or multiple subgroups of interest are planned.

Responder analyses and other categorical analyses will be based on the CMH test or Fisher's exact test, as appropriate and if the data allow. Continuous endpoints will be evaluated using ANCOVA or ANOVA model methodology, as appropriate and if the data allow.

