ⁱ TWO early morning (30-45 minutes after awakening for the day) and TWO late night (10 PM - 12 AM; 22:00-00:00) saliva collections for salivary cortisol should be performed during the screening period within 28 days of enrollment into the open-label dose-escalation period and results reviewed for eligibility prior to enrollment. Subjects who require wash-out of medications should perform these collections AFTER wash-out. A visiting nurse may assist with processing and shipping the Screening and Day 41, 42, 50, 51, 64 (if applicable), 65 (if applicable), and 79 saliva collections to the central laboratory; or the subject may submit these to the study site for shipping to the central laboratory, per subject preference (all other collections should be brought by the subject to the next visit at the study site).

^j For subjects in the double-blind randomized withdrawal period, if the mean Day 64/65 24-hr UFC result is available prior to or at the time of R2, study completion assessment will be performed: if subjects are found to have met criteria for completing the study (i.e., 24-hr UFC is $>$ 1.3 \times ULN and has also increased by $>$ 50% relative to the mean Day 50/51 24-hr UFC), R3 will be conducted, rather than R2 (i.e., the subject will skip R2). If the mean Day 64/65 24-hr UFC does not meet criteria for completing the study, or the result is not available at the time of R2, the subject will proceed with R2.

^k Adverse events will be collected from the time the subject signs the informed consent form until the last study visit or 30 days after the last dose of study drug, whichever is later.

11-DOC, 11-deoxycorticosterone; 17-OHP, 17-hydroxyprogesterone; A, aldosterone; A4, androstenedione; ACTH, adrenocorticotrophic hormone; aPTT, activated partial thromboplastin time; demog, demographics; DHEA, dehydroepiandrosterone; DHEAS, dehydroepiandrosterone sulfate; ECG, electrocardiogram; ET, Early Termination; excl, exclusion; HbA1c, hemoglobin A1c; HBsAg, hepatitis B surface antigen; HCV, hepatitis C virus; HIV, human immunodeficiency virus; incl, inclusion; INR, international normalized ratio; P, progesterone; PE, physical examination; PK, pharmacokinetic(s) (samples); PT, prothrombin time; SHBG, sex hormone binding globulin; T, testosterone; tel, telephone visit; UFC, urinary free cortisol; ULN, upper limit of normal

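### The two proportion-normal late-night salivary cortisol endpoints set no baseline condition, although exclusion 3 lets subjects with a normal screening value enrol

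*Protocol*

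**What the plan says.** Entry. Exclusion 3 in Protocol section 4.2 (repeated in the Synopsis) reads "Normal late night salivary cortisol value during screening unless the subject's history clearly demonstrates that he or she does not have pseudo-Cushing's or cyclic Cushing's". It goes on to say that when the investigator judges that neither condition is present, "the subject may be enrolled with approval of the medical monitor". No limit is set on the number admitted this way.

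Endpoints. Section 9.6.1.2 and the Synopsis list two responder endpoints for late-night salivary cortisol. One is "The proportion of subjects with a normal late night salivary cortisol at the end of the double-blind randomized withdrawal period". The other covers the open-label periods and begins "The proportion of subjects with a normal late night salivary cortisol at the end of the open-label dose-escalation period"; it continues to the end of the additional open-label period. Neither mentions the baseline value.

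Population and test. The preamble to the list says the endpoints will be evaluated "for the ITT population as a whole and for each baseline UFC stratum", if the data allow and unless the SAP says otherwise. Section 9.6.2.2 adds that "Responder analyses and other categorical analyses will be based on the CMH test or Fisher's exact test" and names no adjustment for baseline salivary status.

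Baseline data. Section 6.10.1.2 and the Appendix 1 footnotes call for two early-morning and two late-night samples, taken after any wash-out: "saliva collections for salivary cortisol should be performed during the screening period within 28 days of enrollment into the open-label dose-escalation period".

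Contrast with UFC. Inclusion 3 requires a mean baseline UFC of 1.3 to 10 × ULN. Exclusion 4 begins "Normal 24-hr UFC during screening (this would be suggestive of cyclic Cushing's" and has no waiver.

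**The concern.** For UFC, the entry criteria guarantee that every eligible subject starts abnormal, so a normal value at period end means that the value has been normalized. The salivary endpoints use the same form of words, but the entry criteria do not give the same guarantee. The waiver is written for subjects with a normal screening value, so their presence is foreseen by the protocol and is not a deviation.

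A subject normal before the first dose who stays normal is counted alongside one whose value fell into the normal range on treatment. In the open-label periods there is no control arm to show how much of the proportion was present from the start. In the randomized period such subjects tend to be normal on either treatment, so they carry little information about the contrast while filling places in a very small comparison.

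**Working it through.** The protocol gives no expected salivary response rate and no power (section 9.2 states that no formal sample size calculation was made), so there is no planned figure to reproduce. The check sets the entry rule against the endpoint definition and then illustrates the size under stated assumptions.

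**Can a subject with a normal baseline enter and be counted?**
- Entry: yes, through the exclusion 3 waiver.
- Endpoint: counted if normal at period end, with nothing excluded on baseline status.
- Analysis: CMH or Fisher's exact test, overall and by UFC stratum, with no salivary baseline term stated.

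**Open-label illustration.** Let f be the share of subjects normal at baseline who stay normal (assumed), and r the true normalization rate among those elevated at baseline (assumed).

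Apparent rate = f + (1 − f) × r

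With all 16 planned subjects in the denominator:

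| Normal at baseline | f | r = 0 | r = 25% |
|---|---|---|---|
| 0 of 16 | 0% | 0% | 25.0% |
| 1 of 16 | 6.25% | 6.25% | 29.7% |
| 2 of 16 | 12.5% | 12.5% | 34.4% |
| 4 of 16 | 25% | 25.0% | 43.8% |

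For example, 0.125 + 0.875 × 0.25 = 0.344. The excess over r is f × (1 − r), so it is largest when the drug does least.

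**Smaller sets.** The denominator of 16 fits only the dose-escalation period with every enrolled subject counted. Section 9.3 defines ITT as randomized and dosed subjects, and the additional open-label period takes only those not randomized. If 6 to 10 of the 16 are randomized (assumed), 10 to 6 remain for the additional open-label period, where one subject is worth 1/10 to 1/6, or 10 to 17 points. The randomized arms would then hold 3 to 5 subjects each, where one subject is worth 1/5 to 1/3, or 20 to 33 points of that arm's proportion.

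**Randomized illustration.** If the same share f is normal at baseline in both arms and stays normal, each arm's rate becomes f + (1 − f) × r, and the true difference is multiplied by (1 − f). With assumed rates among baseline-elevated subjects of 80% on ATR-101 and 10% on placebo, and the most favourable case of all 16 randomized (8 per arm), exact enumeration of Fisher's test at two-sided 5% gives:

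| f | ATR-101 | Placebo | Difference | Power |
|---|---|---|---|---|
| 0% | 80.0% | 10.0% | 70 points | 79% |
| 12.5% | 82.5% | 21.3% | 61 points | 62% |
| 25% | 85.0% | 32.5% | 53 points | 45% |

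The direction is dilution: 0.875 × 70 = 61.25 and 0.75 × 70 = 52.5.

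**The case against.** The strongest reply is that this belongs in the SAP. The preamble in section 9.6.1.2 defers to the SAP, and section 9.1 leaves the technical detail there. Restricting a responder denominator to subjects abnormal at baseline would be an ordinary SAP provision, and the SAP was not available for this review. This stands in part: a SAP fixed before unblinding is an acceptable place for the correction. It does not remove the point, because the protocol itself states the endpoint, names the population and creates the waiver. If the SAP is silent, the definition as written governs.

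A second reply is that nothing is literally misstated. The protocol describes status at period end and does not call it normalization or success. That is true, but a status that some subjects may hold before dosing is weak evidence of efficacy in an uncontrolled period.

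Several replies limit the size, and they stand:
- The number of subjects admitted under the waiver is not given. Entry needs a clear history, the investigator's view and medical monitor approval, so it may be zero.
- Admission under the waiver is not the same as a normal baseline. Two late-night samples are taken, and one normal value can trigger exclusion 3 while the mean stays above ULN.
- A rate of 0% under no drug effect is a simplification. A subject elevated at baseline can give a normal sample through ordinary variation, so even the restricted open-label proportion is not a pure drug effect.
- The change and percentage-change endpoints for late-night salivary cortisol are on the same list. A subject who starts and stays normal would not stand out as improved there.

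**Conclusion.** The concern holds in a limited form. The two proportion-normal salivary endpoints do not require an abnormal start, and exclusion 3 does not ensure one. Any subject with a normal baseline can raise the open-label proportions without a drug effect. With 1 or 2 such subjects among 16 in dose escalation the addition is about 6 or 12.5 points under no drug effect, and each weighs more in the smaller sets. These figures assume that the subjects stay normal and that no baseline-elevated subject becomes normal by chance. The power figures also assume 80% versus 10% and 8 per arm, none of which is in the protocol.

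A reader might infer three stronger things that the text does not support:
- That the randomized comparison is biased in favour of ATR-101. Allocation is by chance, so the expected effect is dilution. An uneven split is the ordinary chance imbalance of a small trial.
- That every subject admitted under the waiver is a spurious success. Some may have a mean baseline above ULN.
- That the main efficacy conclusion is at risk. Only secondary endpoints are affected; the primary endpoint rests on UFC, where inclusion 3 and exclusion 4 ensure an abnormal start.

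**What to change.** In section 9.6.1.2 and the Synopsis, or in the SAP before unblinding:
- Evaluate the two proportion-normal endpoints among subjects whose baseline late-night salivary cortisol was above ULN, with baseline defined as the mean of the post-wash-out screening samples.
- Show the whole-population proportion by baseline status as a supportive display.
- Keep all subjects in the change and percentage-change analyses.

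This takes a sentence or two. The screening samples are already required, and no eligibility rule, visit or treatment changes. The cost is a slightly smaller denominator for two secondary endpoints. If no subject enrols with a normal baseline, the restriction changes nothing.

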6.3. Eligibility

Review of study inclusion/exclusion criteria will be done at/after the screening visit (Visit S1), before enrolling the subject into the open-label dose-escalation period at Visit T1 and before either randomizing the subject or enrolling the subject into the additional open-label dosing period at Visit R1/A1. Please note that prior to enrolling the subject into the open-label dose-escalation period, regarding the laboratory values, only the Visit T1 pregnancy test (if applicable and if performed at the site), and the Visit S1 hematology, chemistry, PT, PTT, INR, HbA1c, lipid panel, serology, pregnancy test (if applicable), urinalysis, urine drug screen, 24-hr UFC, and salivary cortisol levels need to be reviewed. The screening blood hormone levels are for baselining purposes and the results do not need to be available prior to enrolling the subject.

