7.3.1. Visit R1 (Day 57)

Prior to Visit R1, the Investigator should review the baseline 24-hr UFC level (calculated as the mean of all 24-hr UFC levels obtained within the 28 days prior to enrollment into the open-label dose-escalation period) and compare it to the mean Day 50/51 24-hr UFC result to determine whether the subject meets criteria to enter the double-blind randomized withdrawal period of the study (the subject is eligible if the mean Day 50/51 24-hr UFC is \leq ULN or \leq 50% of the baseline value). If the subject does not meet criteria to enter the double-blind randomized withdrawal period, the subject should instead enter an additional 4-week open-label dosing period, described in Section 7.4.

At Visit R1, appropriate study site personnel should:

- Receive the Day 56 saliva collections and 24-hr urine collection (and any other collections that were not previously submitted) from the subject and submit these to the central laboratory for analysis.
- Record adverse events and update medications.
- Record vital signs and weight.
- Perform a complete PE.
- Obtain a 12-lead ECG.
- Collect fasting blood samples for hematology, chemistry, PT, aPTT, INR, insulin, HbA1c, lipid panel, hormones (11-DOC, 17-OHP, A, A4, ACTH, cortisol, DHEA, DHEAS, free T, P, renin, SHBG and total T) and PK within 30 minutes prior to administration of study drug.

- All blood hormone collections should be performed between 6-10 AM (06:00-10:00), as close to 8 AM (08:00) as practicable.
- Subjects need to be in a seated position for at least 15 minutes prior to collection of blood hormone levels so that renin and aldosterone levels are stable.
- If the subject is not fasting, proceed with the visit but mark the sample collection as being non-fasting.
- Collect a urine sample for urinalysis and, if the subject is a woman of childbearing potential, perform a urine pregnancy test (preferred; or submit a serum or urine sample to a laboratory for pregnancy testing if required by your institution/IRB/EC).
- Record the date and time of the subject's last previous study drug dose (expected to have occurred the evening prior to the visit).
- Collect study drug and assess compliance.
- Confirm that the subject meets criteria for randomization into the double-blind randomized withdrawal period of the study. If not, enroll the subject into the additional open-label dosing period of the study, described in Section 7.4.

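### At the end of withdrawal, hormone and metabolic endpoints are referenced only to pre-study baseline, so change since randomization is not an endpoint and run-in variation may add noise

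*Protocol*

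**What the plan says.** Section 9.6.1.2 has the secondary endpoints evaluated at every post-baseline "visit, at the end of the open-label dose-escalation period and at the end of the double-blind randomized withdrawal period", if the data allow and "unless otherwise specified in the Statistical Analysis Plan". The list then uses two different reference points for the double-blind period.

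- UFC: "The change and percentage change in the 24-hr UFC from randomization at the end of the double-blind randomized withdrawal period".
- Late night salivary cortisol: "The change and percentage change in the late night salivary cortisol from randomization at the end of the double-blind randomized withdrawal period".
- Blood hormones: "The change and percentage change from baseline in blood hormone levels, including 11-DOC, 17-OHP, A, A4, ACTH, cortisol", followed by seven more analytes.
- Metabolic measures: "The change from baseline in fasting glucose, insulin, lipid panel, systolic blood pressure, diastolic blood pressure and BMI".

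For the first two, change from baseline is a separate endpoint for the open-label periods. The last two name no period and have no version measured from randomization. The synopsis repeats the same list.

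Baseline here means before study drug. Section 6.3 states: "The screening blood hormone levels are for baselining purposes". Section 9.6.2.1 defines the UFC baseline as a pre-enrollment mean. No sentence defines baseline for the metabolic measures, but under 6.10.1.4 and 6.10.1.5 the screening visit (S1) provides the only fasting set before the first dose.

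Section 7.3.1 provides a full set at randomization, before the first blinded dose: "Collect fasting blood samples for hematology, chemistry, PT, aPTT, INR, insulin, HbA1c, lipid panel, hormones", with vital signs and weight. Section 9.6.2.2 allows ANCOVA or ANOVA for continuous endpoints and names no covariate.

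**The concern.** The double-blind withdrawal period is the only placebo-controlled part of the study. What differs by assignment begins at R1. A change from pre-study baseline to the end of that period adds the open-label run-in change to the change after randomization, and only the second depends on the arm. Two consequences follow.

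- Differences between subjects in their run-in response, and any drift since screening, can enter the comparison as noise. About 16 subjects are to be enrolled, so at most about 8 per arm can be randomized, and fewer if some miss the Day 50/51 criteria.
- The contrast in section 1.3, effect kept on ATR-101 versus lost on placebo, is not itself an endpoint for these variables. They carry three secondary objectives in section 2.2: adrenal steroids and intermediates, ACTH, and metabolic parameters.

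The protocol already applies the other rule to UFC and salivary cortisol and gives no reason for the split.

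**Working it through.** The protocol gives no SD, correlation, effect size or sample-size calculation for these variables, so there is no figure to reproduce. The correlations below are assumptions.

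**Timing.** Day 1 to Day 85 is 84 days, or 12 weeks. S1 may be up to 56 days before enrollment (section 7.1), so the pre-study value can be 84 + 56 = 140 days, or 20 weeks, old. R1 (Day 57) to Day 85 is 28 days, or 4 weeks. For subjects needing wash-out, 7.1 postpones the hormone sample but does not say the same for insulin and lipids.

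**Decomposition.** Let Y0, Y1 and Y2 be the pre-study, R1 and end values. Then Y2 − Y0 = (Y1 − Y0) + (Y2 − Y1). The first term precedes randomization and has the same expectation in both arms, so it cancels in expectation from the arm difference.

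A simulation confirms this (20,000 runs, 8 per arm, shared run-in shift −1 SD, true arm difference 0.8 SD, correlations Y0–Y1 0.6, Y0–Y2 0.5, Y1–Y2 0.8):

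- The estimated arm difference is 0.80 with either reference.
- The standard error is 0.50 from baseline and 0.32 from R1. Check: the SD of a change is √(2(1 − r)), giving 1.00 and 0.63; multiplied by √(2/8) this is 0.50 and 0.32.
- Mean change from baseline is −1.00 on ATR-101 and −0.20 on placebo. From R1 it is 0.00 and +0.80.

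**Size under assumed correlations.** Let r0 be the correlation of the pre-study value with the end value, and r1 that of R1. The ANCOVA residual SD ratio (R1 versus pre-study covariate) is √((1 − r1²)/(1 − r0²)). The change-score SD ratio is √((1 − r1)/(1 − r0)).

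| r0 | r1 | ANCOVA SD ratio | Change-score SD ratio |
|---|---|---|---|
| 0.3 | 0.6 | √(0.64/0.91) = 0.84 | √(0.4/0.7) = 0.76 |
| 0.4 | 0.7 | √(0.51/0.84) = 0.78 | √(0.3/0.6) = 0.71 |
| 0.5 | 0.8 | √(0.36/0.75) = 0.69 | √(0.2/0.5) = 0.63 |
| 0.6 | 0.6 | 1.00 | 1.00 |
| 0.7 | 0.5 | √(0.75/0.51) = 1.21 | √(0.5/0.3) = 1.29 |

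The first three rows give the 16–31% reduction in ANCOVA residual SD. Crossing the ends of the ranges widens it: r0 = 0.5 with r1 = 0.6 gives √(0.64/0.75) = 0.92, and r0 = 0.3 with r1 = 0.8 gives √(0.36/0.91) = 0.63.

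**When the gain vanishes.** Suppose a stable subject level, an individual drug effect d, independent visit noise e of equal variance, full maintenance on ATR-101, and loss of a fraction f of the effect on placebo. Adding the change variances of the two arms gives:

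- from baseline: Var(d)[1 + (1 − f)²] + 4Var(e);
- from R1: Var(d)f² + 4Var(e).

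The difference is Var(d)[1 + (1 − f)² − f²] = 2(1 − f)Var(d). It is zero at full reversal (f = 1), favours R1 if reversal is partial (f < 1), and favours baseline if placebo values overshoot (f > 1). Drift between the pre-study sample and R1 adds variance only to change from baseline.

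**Role of the covariate.** If ANCOVA includes both the pre-study and the R1 value, the treatment estimate is the same for either absolute change score (0.83 in size for both in one simulated data set). With R1 alone the two differ (0.72 from baseline, 0.81 from R1). The identity does not extend to percentage change, whose denominators differ.

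**The case against.** The strongest reply is that this belongs to the SAP. Section 9.6.1.2 lets the SAP specify otherwise, 9.6.2.2 leaves the model open, and an ANCOVA with both earlier values makes the choice of absolute change score irrelevant. The SAP is not at hand and may settle it. This stands in part: nothing in the protocol prevents a good analysis. But the reference point is stated rather than left open, it differs within one list, and ANCOVA or ANOVA with no named covariate does not secure the repair.

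A second reply is that change from baseline suits the hypothesis. Section 1.3 is framed around baseline, the primary endpoint also uses it, and evaluation at each post-baseline visit would show the change at both R1 and R3. That is fair. A placebo mean near zero is a legitimate picture of return, and for absolute change in the same subjects the two means can be subtracted. Subtraction gives neither the standard error nor the percentage change from R1.

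A third reply is that the precision gain is conditional. This is correct. With full reversal on placebo and full maintenance on ATR-101, the model above gives no gain at all.

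A reader might infer that the placebo comparison is biased by the run-in. It is not, because the run-in change precedes randomization and cancels in expectation. A reader might also turn the midpoint case (0.4 versus 0.7) into a claim that the plan forfeits about 1.6 times as many subjects (0.84/0.51 = 1.65). The protocol supplies no correlation for any of these variables, and one assumed range cannot serve BMI, lipids, ACTH and renin alike.

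**Conclusion.** The point holds as a modest, inexpensive improvement to secondary endpoints. The comparison between arms is unbiased as written, and the primary endpoint is not affected. The two defects are that change since randomization is not an endpoint for hormones and metabolic measures, and that run-in variation may add noise in a sample of at most about 16 randomized subjects.

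A precision gain from R1 is likely if reversal over 4 weeks is partial, or if values drift over the 12–20 weeks since the pre-study sample. Its size is not derivable from the documents. The 16–31% figure rests wholly on the assumed correlations, and the gain is zero or negative if the pre-study value predicts the end value as well or better. The gap in the endpoint definition remains whatever the correlations are.

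**What to change.** In section 9.6.1.2 and the synopsis, for the double-blind period, add change from randomization (R1) for the blood hormones (with percentage change), fasting glucose, insulin, lipids, blood pressure and BMI. Name ANCOVA with the R1 value as covariate, optionally with the pre-study value as well. Keep change from baseline as the endpoint for the open-label periods and as a descriptive summary at the end of withdrawal.

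The cost is wording and a few more tables; the R1 values are already collected. Each covariate uses one degree of freedom. With 16 randomized, the residual degrees of freedom fall from 14 (16 − 2, arm only) to 13 with R1 and 12 with both. With only 8 randomized they fall from 6 to 5 and 4, which is a reason to treat the second covariate as optional.
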